7.1.7.3. Confirmed Virologic Failure

Participants with confirmed virologic failure (CVF) must be discontinued from study treatment. However, participants who have received at least one dose of CAB LA or RPV LA prior to confirming virologic failure will remain in the study on oral HAART in the LTFU Phase.

A plasma sample from the suspected virologic failure visit as well as Day 1 (if baseline HIV-1 RNA level ≥ 200 c/mL) will be sent for genotypic and phenotypic resistance testing and the result made known to the Investigator when available. A plasma sample from the confirmation visit will be obtained for storage. This sample may be used for possible future analyses, e.g., for genotypic and phenotypic analyses of participants who experience virologic failure.

For all participants who meet CVF, baseline and suspected virologic failure plasma samples with HIV-1 RNA level ≥ 200 c/mL will be analyzed in an attempt to obtain genotype/phenotype data on as many samples as possible. Plasma samples for storage will also be obtained at unscheduled visits including confirmation of CVF. Participants may continue to receive study drug at the discretion of the investigator until results of resistance testing are available at which time the participant must be discontinued from the study. Even if genotype/phenotype data cannot be generated, participant must also be discontinued from the study treatment.

If a participant is prematurely discontinued from the study treatment, the investigator must make every effort to perform the Withdrawal Visit evaluations outlined in the Time and Events. These data will be recorded as they comprise essential evaluations needed to be done before discharging any participant from the study.

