6.9. Interruption of Study Intervention and Visit/Dosing Windows

IP may be interrupted at the discretion of the Investigator in the event of an AE, according to the severity of the AE.

If one or more antiretroviral medications is held due to toxicity or adverse events, all antiretroviral medications must be held to reduce the risk of development of resistance taking into account both the length of the planned interruption and the pharmacokinetic half-life of each antiretroviral of the regimen, in a way to minimize the risk of development of resistance.

It is important to note that keeping to the participant's visit schedule is a very important component to the study.

Note: All decisions regarding dose interruption / resumption must be discussed with the medical monitor in advance.

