6.9.1. IM Dosing

Participants receiving CAB LA and/or RPV LA are anticipated to be at risk for development of virologic resistance if ART is interrupted. The time period during which participants are at risk for development of virologic resistance may be determined by the period between when drug levels fall below therapeutic values and when they fall below levels which exert selective pressure on HIV. This time period will vary by ART agent and is dependent upon effective concentration, inhibitory concentration, and half-life. Plasma concentrations of both LA drugs may be measurable for more than one year following IM injections. Any interruption in IM dosing should be discussed with the Medical Monitor. Investigators should ensure that the participant initiates alternative highly active ART to minimize the risk of developing resistance as concentrations of CAB and RPV decline over time.

IM dosing is expected to occur during the week in which the participant's projected visit falls (as according to the date of the first injection). The first injections for participants who choose to start injections immediately will occur at Day 1. The first injections for participants electing to participate in the oral lead are administered at Month 1 (can be performed before lab results become available), and the second injections are given at Month 2.

The participant's projected visit is determined by their first injection date and, ideally, is the same date for every injection. For example, if the 1st dose (Month 1) is January 15th, then dose 2 (Month 2) will be February 15th, and dose 3 (Month 4) will be April 15th, etc.

Since the first injection visit (Day 1 or Month 1) will determine the future injection visit schedule for participants, planning for the first injection visit date (within allowed visit windows) should take into consideration the availability of the participants to adhere to future visit windows (planned vacations, business trips, weekends, holidays, *etc.*).

Dosing for participants randomized to CAB LA + RPV LA is as follows:

All injections should be planned as single injections per drug.

6.9.1.1. IM injections every 2 months (Oral Lead In):

Month 1 – CAB LA 600 mg + RPV LA 900 mg IM, each given as 1 X 3 mL IM injection

Month 2 - CAB LA 600 mg + RPV LA 900 mg IM, each given as 1 X 3 mL IM injection

Month 4 and Q2M thereafter - CAB LA 600 mg + RPV LA 900 mg IM, every 2 months until Month 12, each given as 1 X 3 mL IM injection

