7.1.2. Liver chemistry stopping criteria

Study treatment or Investigational Product must stop immediately when participant meets one of the criteria described in Table below:

Table 3 Liver Chemistry Stopping Criteria - Liver Stopping Event for phase III - IV studies

Liver Chemistry Stopping Criteria - Liver Stopping Event	
If Baseline ALT ≤ 1.5x ULN	
ALT-absolute	ALT ≥ 8xULN
ALT Increase	ALT ≥ 5xULN but <8xULN persists for ≥2 weeks (with bilirubin <2xULN and no signs or symptoms of acute hepatitis or hypersensitivity)
Bilirubin^{1,2}	ALT ≥ 3xULN and bilirubin ≥ 2xULN (>35% direct bilirubin)
Cannot Monitor	ALT ≥ 5xULN but <8xULN and cannot be monitored every 1 - 2 weeks
Symptomatic³	ALT ≥ 3xULN with symptoms (new or worsening) believed to be related to liver injury or hypersensitivity
If Baseline ALT > 1.5x ULN	
ALT-absolute	ALT ≥ 5x baseline OR > 500 U/L (whichever occurs first)
ALT Increase	ALT ≥ 3x baseline but <5x baseline persists for ≥2 weeks (with bilirubin <2xULN and no signs or symptoms of acute hepatitis or hypersensitivity)
Bilirubin^{1,2}	ALT ≥ 3x baseline OR > 300 U/L (whichever occurs first) and bilirubin ≥ 2xULN
Cannot Monitor	ALT ≥ 3x baseline but <5x baseline and cannot be monitored every 1 - 2 weeks
Symptomatic³	ALT ≥ 3x baseline and symptoms (new or worsening) believed to be related to liver injury or hypersensitivity.

1. Serum bilirubin fractionation should be performed if testing is available. If serum bilirubin fractionation is not immediately available, discontinue study intervention for that participant if ALT ≥3xULN **and** bilirubin ≥2xULN. Additionally, if serum bilirubin fractionation testing is unavailable, **record presence of detectable urinary bilirubin on dipstick**, indicating direct bilirubin elevations and suggesting liver injury.
2. All events of ALT >3xULN and bilirubin >2xULN (>35% direct bilirubin) must be reported as an SAE (excluding studies of hepatic impairment or cirrhosis); INR measurement is not required, and the threshold value stated will not apply to participants receiving anticoagulants.
3. New or worsening symptoms believed to be related to liver injury (such as fatigue, nausea, vomiting, right upper quadrant pain or tenderness, or jaundice) or believed to be related to hypersensitivity (such as fever, rash or eosinophilia).

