7.1.2.1. Liver Chemistry Stopping Criteria, Participant Management and Follow-Up

Participants who develop ALT $\geq 5 \times$ ULN must be followed weekly until resolution or stabilization (ALT $< 5 \times$ ULN on 2 consecutive evaluations).

When any of the liver chemistry stopping criteria is met, do the following:

- Immediately hold IP. If on LA therapy, **do not** administer another injection until approval is received from the ViiV Safety and Labelling Committee.
- Report the event to the Medical Monitor within 24 hours of learning its occurrence.
- Complete the liver event eCRF and SAE eCRF, where applicable.
- Complete the liver imaging and/or liver biopsy eCRFs if these tests are performed.
- Perform liver event follow up assessments (described below), and monitor the participant until liver chemistries resolve, stabilize, or return to Baseline values as described below.
- Make every reasonable attempt to have participants return to clinic within 24 hours for repeat liver chemistries, liver event follow-up assessments (see below), and close monitoring.
- A specialist or hepatology consultation is recommended.
- Monitor participants twice weekly until liver chemistries (ALT, AST, alkaline phosphatase, bilirubin) resolve, stabilize or return to within Baseline values.

Make every attempt to carry out the **liver event follow-up assessments** described below:

- Viral hepatitis serology including:
 - Hepatitis A immunoglobulin M (IgM) antibody;
 - Hepatitis B surface antigen (HBsAg) and Hepatitis B Core Antibody (IgM);
 - Hepatitis C RNA;
 - Hepatitis E IgM antibody;
 - Cytomegalovirus IgM antibody;
 - Epstein-Barr viral capsid antigen IgM antibody (or if unavailable, obtain heterophile antibody or monospot testing);
- Syphilis screening;
- Drugs of abuse screen including alcohol;
- Serum acetaminophen test (N-acetyl-para-aminophenol [APAP] adduct test). The site must contact GSK when this test is required. Please refer to the central laboratory manual.

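### Protocol Section 7.1.7.3 both ends study treatment at confirmed virologic failure and lets study drug continue until resistance results, with no exception for a long-acting injection

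*Protocol*

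**What the plan says.** Section 7.1.7.3 opens with a plain stop: "Participants with confirmed virologic failure (CVF) must be discontinued from study treatment". It then deals with participants who have already been injected; they "will remain in the study on oral HAART in the LTFU Phase".

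The third paragraph is addressed to everyone who meets CVF. It says "Participants may continue to receive study drug at the discretion of the investigator until results of resistance testing are available". The same sentence then closes with a further requirement: "at which time the participant must be discontinued from the study". The sentence after that, for cases where no genotype or phenotype can be generated, speaks of study treatment, not of the study.

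Other sections bear on how this is read:

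- **Section 6** counts CAB LA and RPV LA as investigational product alongside the oral tablets.
- **Section 4.1.4** asks for HAART within 8 weeks (±7 days) of the last injection, starts the 52-week LTFU on the day of the last long-acting dose, and treats people in LTFU as on study but off product.
- **Section 6.9** says "All decisions regarding dose interruption / resumption must be discussed with the medical monitor in advance". Section 6.9.1 adds Medical Monitor agreement for dosing outside the window.
- **Section 7.1.2**, on liver events, says "Study treatment or Investigational Product must stop immediately when participant meets one of the criteria described in Table below". Section 7.1.2.1 tells sites treating someone on long-acting therapy not to "administer another injection until approval is received from the ViiV Safety and Labelling Committee".
- **Section 8.8.1** says resistance results go to the investigator to help choose the next regimen.

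**The concern.** The third paragraph treats a daily tablet and a two-monthly injection alike. Oral drug continued while a result is pending can be stopped on the day the result arrives. An injection cannot be taken back: Section 2.3.1 says residual CAB can persist for more than a year in some cases, and Section 6.9.1 says the same of both long-acting drugs. Outside the oral lead-in and oral bridging, a participant in the injectable arm receives study drug only by injection, so for that person the permission is in practice permission for another injection.

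At stake is a further long-acting dose of a regimen already confirmed as failing, and a later start of the HAART that Section 2.3.1 names as the mitigation against resistance. The closing words about leaving the study also contradict the LTFU rule two paragraphs above them.

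**Working it through.** **Does any other text remove the injection?**

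| Place | What it does | Bars an on-schedule injection after CVF? |
|---|---|---|
| 7.1.7.3, first paragraph | Ends study treatment; injected participants go to oral HAART in LTFU | By implication, but the third paragraph then allows a delay |
| 2.3.1 (treatment failure) and 7.1 | Require discontinuation at CVF | No timing given |
| 6.9, 6.9.1 | Medical Monitor contact for interruption, resumption or out-of-window dosing | No; an on-schedule dose triggers none of these |
| 7.1.7.2 | Study team contact about interruptions; Medical Monitor when the site sees a need | No |
| 4.1.4 | Medical Monitor discussion of the HAART choice; HAART time limit | No; see the dates below |
| 7.1.2.1 (liver) | Forbids another injection before approval | Yes, but for liver events only |

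So the permission in the third paragraph stands beside the stop in the first, and nothing else settles which governs an injection.

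**Can an injection fall due before the HAART limit?** Count days from a last injection given on its projected date.

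- Under Section 6.9.1 the "projected visit is determined by their first injection date and, ideally, is the same date for every injection". Two calendar months on the same date is 59 to 62 days.
- Next two-monthly injection: day 59–62. With ±7 days, the window opens on day 59 − 7 = 52 to 62 − 7 = 55 and closes on day 59 + 7 = 66 to 62 + 7 = 69.
- HAART limit in Section 4.1.4: 8 × 7 = day 56; outer limit 56 + 7 = day 63.
- The on-schedule injection precedes the outer HAART limit by 63 − 62 = 1 to 63 − 59 = 4 days. Its window opens 63 − 55 = 8 to 63 − 52 = 11 days before that limit.

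**If that injection is given**, the last-injection date moves:

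- New HAART limit: 59 + 56 = day 115 to 62 + 56 = day 118.
- New outer limit: 59 + 63 = day 122 to 62 + 63 = day 125.
- Shift: 59 to 62 days. The 52-week LTFU clock restarts by the same amount.

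The HAART limit therefore does not prevent the injection; giving the injection postpones the limit.

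**Would withholding it leave a gap in ART?** HAART started at the outer limit, day 63, is 1 to 4 days after the nominal injection date and before the injection window closes (day 66–69). That is within the delay the dosing schedule already accepts.

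**The closing phrase.** Removal from the study fits BIK participants and those who stop during the oral lead-in, because they have no LTFU. For anyone injected it conflicts with the first paragraph of 7.1.7.3, with 4.1.4 and with 7.1, all of which keep that person on study in LTFU. The next sentence's use of study treatment points to a slip.

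**The case against.** The strongest reply is that the section can be read coherently. The first paragraph already has a rule specific to injected participants, and it sends them to oral HAART. The later permission ends with removal from the study, which is literally right only for people with no LTFU, so it could be meant for oral participants alone. Section 2.3.1 also describes transfer to oral HAART at CVF. This reading is available, and a cautious site may well follow it. It is not compelled: the third paragraph is addressed to all who meet CVF and names no formulation.

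Second, waiting is defensible. Results guide the next regimen, and Section 6.9.1 describes falling drug levels as a hazard in themselves, which weakens the liver comparison because there the drug is the suspected cause. This stands as a reason for allowing some delay. It does not explain why an irreversible dose should be covered without being mentioned.

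Third, the dates show only that an injection could fall due while results are pending. Turnaround is not stated, and testing uses the sample from the suspected-failure visit, drawn before confirmation. That limit is accepted.

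A reader might infer more: that the protocol directs injections after CVF, that injected participants lose their LTFU, or that the primary comparison is affected. The text supports none of these. The clause is discretionary, the surrounding sections keep injected participants in LTFU, and every CVF participant must come off study treatment on either reading.

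**Conclusion.** Section 7.1.7.3 is internally inconsistent on what happens between CVF and the resistance result. As worded, a site could give an on-schedule long-acting injection to a participant already confirmed as failing, which would move the HAART limit and the LTFU start by 59 to 62 days.

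This rests on reading study drug to include the long-acting products, as Section 6 does for investigational product, and on a two-monthly dose falling due before results return. The number of participants exposed cannot be derived, since the protocol gives neither a resistance-test turnaround nor an expected CVF rate. The primary endpoint is unaffected. The closing phrase is a wording error that surrounding text largely resolves.

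This is a cheap patient-safety improvement, not a flaw in the trial's inference.

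**What to change.** Amend Section 7.1.7.3 as follows:

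1. Limit the permission to continue pending resistance results to participants on daily oral study drug: BIK, or the oral lead-in before any injection.
2. State that once CVF is confirmed no further CAB LA or RPV LA injection is given. Injected participants start oral HAART, chosen with the Medical Monitor, within 8 weeks (±7 days) of the last injection, and the regimen is adjusted when resistance results arrive.
3. Replace removal from the study with removal from study treatment, and add that injected participants enter LTFU.

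The cost is wording in one section. The real downside is that HAART may sometimes have to be chosen before the results that Section 8.8.1 provides to guide it, and the investigator loses discretion over one injection. Because the HAART limit in Section 4.1.4 already applies, withholding the injection need not leave a gap in therapy.

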7.2. Lost to Follow Up

A participant will be considered lost to follow-up if he or she repeatedly fails to return for scheduled visits and is unable to be contacted by the study site.

The following actions must be taken if a participant fails to return to the clinic for a required study visit:

- The site must attempt to contact the participant and reschedule the missed visit as soon as possible and counsel the participant on the importance of maintaining the assigned visit schedule and ascertain whether or not the participant wishes to and/or should continue in the study.
- Before a participant is deemed lost to follow up, the investigator or designee must make every effort to regain contact with the participant (where possible, 3 telephone calls and, if necessary, a certified letter to the participant's last known mailing address or local equivalent methods). These contact attempts should be documented in the participant's medical record.
- Should the participant continue to be unreachable, he/she will be considered to have withdrawn from the study.

Discontinuation of specific sites or of the study as a whole are handled as part of [Appendix 1](#).

8. STUDY ASSESSMENTS AND PROCEDURES

Protocol waivers or exemptions are not allowed with the exception of immediate safety concerns. Therefore, adherence to the study design requirements, including those specified in the SoA, are essential and required for study conduct.

This Section lists the procedures and parameters of each planned study assessment. The exact timing of each assessment is listed in the SoA, Section [1.3](#)

The following points must be noted:

- If assessments are scheduled for the same nominal time, THEN the assessments should occur in the following order:
 1. 12-lead ECG
 2. vital signs
 3. blood draws

Note: The timing of the assessments should allow the blood draw to occur at the exact nominal time.

- The timing and number of planned study assessments may be altered during the course of the study based on newly available data to ensure appropriate monitoring.
- The change in timing or addition of time points for any planned study assessments must be documented in a Note to File which is approved by the relevant study team member and then archived in the study sponsor and site study files, but this will not constitute a protocol amendment.
- The IRB/IEC will be informed of any safety issues that require alteration of the safety monitoring scheme or amendment of the Informed Consent Form.

8.1. Efficacy Assessments

8.1.1. Plasma HIV-1 RNA

Plasma for quantitative HIV-1 RNA will be collected according to the SoA (Section 1.3). Methods to be used may include but are not limited to the Abbott RealTime HIV-1 Assay lower limit of detection (LLOD) 40 c/mL. ^{CCI}

8.1.2. Lymphocyte Subsets, CD4+ and CD8+

Lymphocyte subsets will be collected for assessment by flow cytometry (total lymphocyte counts, percentage and absolute CD4+ and CD8+ lymphocyte counts, ratios) according to SoA (Section 1.3) and Laboratory Assessments (Section 8.2.2).

8.1.3. CDC HIV-1 Classification and HIV Associated Conditions

HIV-associated conditions will be recorded as per the SoA (Section 1.3). HIV-associated conditions will be assessed according to the 2014 CDC Revised Classification System for HIV Infection (see Section 10.3). When assessing CDC stage at Screening/Baseline, consider only the latest available CD4 T-cell count, except when the participant had an active Stage 3 event 6 months prior to Screening. Indicators of clinical disease progression are defined as:

- CDC Stage 1 at enrolment → Stage 3 event;
- CDC Stage 2 at enrolment → Stage 3 event;
- CDC Stage 3 at enrolment → New Stage 3 Event;
- CDC Stage 1, 2 or 3 at enrolment → Death.

8.2. Safety Assessments

8.2.1. Clinical Evaluations

The following clinical evaluations will be performed according to the Time and Events schedule:

- Monitoring and recording of all AEs and SAEs. Additional information on the Time Period and Frequency of Detecting AEs and SAEs is provided in Section 1.3.
- Physical exams should be conducted as part of normal routine clinical care. Abnormalities noted during any exam must be recorded in the eCRF (e.g., in the current medical conditions or AE logs).
- Height, weight, waist and hip circumference assessments will be measured per the SoA, Section 1.3. Recommended procedures to measure weight, waist and hip circumference can be found in Section 10.10. Appropriate weight related measurements to capture are weight, body fat %, total body water %, muscle mass, and bone mineral mass.

- Vital signs will include systolic and diastolic blood pressure and heart rate collected after resting for about 5 minutes. Temperature will also be collected.
- Past medical history, family history, social history, medication history. Targeted history on cardiovascular risk (smoking history, family and personal history).
- HIV-associated conditions will be recorded.
- Electrocardiogram: A 12-lead ECG will be performed in a semi-supine position after 5 minutes of rest. On Day 1 (Baseline) of the Maintenance Phase, ECGs should be performed in triplicate prior to first dose. An ECG machine that automatically calculates the heart rate and measures PR, QRS, QT, and QTc intervals is preferred (and RR if calculated manually), and these calculated numbers can be used for reporting purposes. Otherwise, an appropriately qualified ECG reader must interpret the results. The same interpreter should assess all ECGs for each participant for the site. Regardless, each ECG should be reviewed by a qualified ECG reader. The qualified ECG reader will make the non-calculated ECG interpretations. The same QT correction formula must be used for each individual participant to determine eligibility for and discontinuation from the study. This formula may not be changed or substituted once the participant has been enrolled.
- Regular monitoring of hematology, blood chemistry, urinalysis and fasting glucose and lipids (parameters to be tested listed below).
- Periodic assessment of glucose, insulin, and bone, cardiovascular, and renal markers;
- Pregnancy testing. A negative urine pregnancy test is required prior to initiation of IP, any dose of CAB LA or RPV LA or as required by the Medical Monitor following a treatment interruption(s). If serum testing is required locally, the results should be available prior to the visit where urine testing is indicated per the SoA (Section 1.3).
- Evaluation and documentation of all concomitant medications and blood products.
- Injection Site Reactions (ISRs) will be assessed clinically during the Maintenance and Extension Phases for the following:
Pain, tenderness, pruritis, warmth, bruising, discoloration, infections, rash, erythema, swelling, induration, and nodules (granulomas or cysts).
- A clinical assessment (using Division of Acquired Immunodeficiency Syndrome [DAIDS] grading scale) should be performed both before and after an injection to identify resolving and new ISRs. All injection site reactions are considered adverse events. The clinical assessment and interpretation of any ISR, will be documented in the ISR AE eCRF.
- Columbia Suicide Severity Rating Scale (eC-SSRS) will be assessed as per the SoA (see Section 1.3 and Suicidal Risk Monitoring Section 8.2.6).

Any appropriately qualified site personnel (e.g., Investigator, sub-Investigator, or study coordinator/nurse) can perform assessments.

